3.7.5.3 Association between biomarkers and clinical outcome

PD-L1 and potential predictors of efficacy

Associations of PD-L1 expression and efficacy outcome (e.g. ORR, DOR and DCR) will be assessed using various approaches, such as tabulations of ORR by PD-L1 expression status, Kaplan-Meier plots and estimates of PFS by PD-L1 expression status, and OS estimates by PD-L1 expression status.

3.8 PD and PK/PD analyses

3.8.1 Immunogenicity

3.8.1.1 Sample ADA Status

Each IG sample is assessed in a three tiered anti-drug anti-body (ADA) testing approach. All IG samples are analyzed in the initial screening assay (first tier). Samples testing negative in the screening assay are not subject to a confirmatory assay. Samples testing positive in the screening assay are then subjected to the confirmatory assay to demonstrate that ADA are specific for the therapeutic protein product (second tier). The titer of confirmatory positive samples will be subsequently determined in the titration assay (third tier). Samples identified as positive in the confirmatory assay are considered ADA positive and are further characterized in the neutralization assay to indicate the presence of neutralizing antibodies (NAb). Samples can test negative in either the screening or confirmatory assay but for analysis purposes they are not differentiated. The following properties of each sample will be provided in the source data:

- Result of assay according to pre-specified confirmatory cut point: ADA positive (yes) or ADA negative (no)
- Titer (for positive samples): numerical representation of the magnitude of ADA response
- Presence of NAb (for positive samples, if NAb assay results are available): yes or no
- Drug tolerance level: highest drug concentration that does not interfere in the ADA detection method
- Fold titer change (i.e. x-fold): threshold for determining treatment boosted

Sample ADA status is determined based on the following definitions:

- *ADA-inconclusive sample*: Sample where assay is ADA negative and PDR001 PK concentration at the time of IG sample collection is greater than or equal to the drug tolerance level or missing.
- *Unevaluable sample*: Sample where assay is not available.
- Determinant sample: Sample that is neither ADA-inconclusive nor unevaluable.

The following definitions apply only to determinant samples:

- o *ADA-negative sample*: Determinant sample where assay is ADA negative and PDR001 PK concentration at the time of IG sample collection is less than the drug tolerance level.
- o *ADA-positive sample*: Determinant sample where assay is ADA positive.
- o *ADA-positive NAb sample*: Determinant sample where assay is ADA positive and presence of NAb = yes.

The following definitions apply only to post-baseline ADA-positive samples with a corresponding determinant baseline sample. To be classified as *treatment-boosted* or *treatment-unaffected*, both the post-baseline and baseline titer must be non-missing:

- o *treatment-induced ADA-positive sample:* ADA-positive sample post-baseline with ADA-negative sample at baseline.
- o *treatment-boosted ADA-positive sample:* ADA-positive sample post-baseline with titer that is at least *the fold titer change* greater than the ADA-positive baseline titer.
- o *treatment-unaffected ADA-positive sample*: ADA-positive sample post-baseline with titer that is less than *the fold titer change* greater than the ADA-positive baseline titer.

NOTE: PK concentrations which are flagged for exclusion will still be used to determine ADA-inconclusive and ADA-negative samples. However, the PK concentrations that are out of long term stability will be excluded from any IG analyses.

The following summaries of ADA sample status (n and %) will be provided using *Immunogenicity prevalence set*:

• ADA-positive samples (i.e. ADA prevalence) and ADA-positive NAb samples, both overall and by time point (including baseline). For summaries by time point, the denominator is the number of subjects at that time point with a determinant sample.

Listings will be provided of sample ADA status (including titer for positive samples).

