2.3.7 Immunogenicity (IG) analysis sets

The Immunogenicity prevalence set includes all subjects in the Full analysis set with a determinant baseline IG sample **or** at least one determinant post-baseline IG sample.

The Immunogenicity incidence set includes all subjects in the Immunogenicity prevalence set with a determinant baseline IG sample and at least one determinant post-baseline IG sample.

See Section 3.8.1 for the definition of determinant.

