2.3.8 Analysis set exclusion

Patients will be excluded from the analysis sets based on the protocol deviations and specific non-protocol deviations entered in the database. All protocol deviations and non-protocol deviations leading to exclusion from specific analysis sets will be identified before database lock. Protocol and non-protocol deviations leading to exclusion from specific analysis sets and reasons for exclusion from populations will be tabulated/listed by treatment (Phase I) /indication and treatment (Phase II).

Table 2-1 displays non-protocol deviations leading to exclusion from analysis set definitions and Table 2-2 displays protocol deviations leading to exclusion from analysis set definitions.

Table 2-1 Non-protocol deviation leading to exclusion from analysis set definitions

Summary of non PD	Analysis set(s) to be excluded
No valid post-baseline safety assessment	SS
No administration of study treatment	FAS, SS, PPS, DDS, DDP, PAS,
	Immunogenicity prevalence set, Immunogenicity incidence set
 Patient, who has not experienced DLT, was not observed for ≥ 28 days following the C1D1 or had not completed the required safety evaluations for Cycle 1 or 	DDS
 Patient who has not experienced DLT, received <70% planned doses at each time of dosing in Cycle 1. 	
The patient did not receive at least one dose of PDR001 during cycle 1 or did not have sufficient PK data in cycle 3 to evaluate the AUC _(0-336h) .	DDP
Patient did not have at least one measurable PDR001 concentration in cycle 1	PAS
No determinant IG sample at both baseline and post-baseline	Immunogenicity prevalence set
No determinant IG sample at baseline or post- baseline or both	Immunogenicity incidence set

Table 2-2 Protocol deviation leading to exclusion from analysis set definitions

Protocol Deviation ID (DVSPID)	Summary of PD	Analysis set(s) to be excluded
INCL01	Written informed consent must be obtained prior to screen procedures.	FAS, SS, PPS, DDS, DDP, PAS, Immunogenicity prevalence set, Immunogenicity incidence set

Novartis	Confidential	Page 22
SAP final CSR	24-Jul-2020 (11:48)	CPDR001X2101

	,	,
Protocol Deviation ID (DVSPID)	Summary of PD	Analysis set(s) to be excluded
INCL04	In the Phase II part, patient does not have at least one tumor lesion meeting measurable disease criteria as determined by RECIST v1.1.	PPS
INCL05	In the Phase II part, patient was not a patient with either NSCLC, melanoma, TNBC, or ATC.	PPS

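### An ADA-negative sample taken before the first dose is called inconclusive if its PK value is missing, although no PDR001 can be present, so the patient needlessly leaves the immunogenicity incidence set

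*SAP*

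**What the plan says.** SAP 3.8.1.1 sorts each immunogenicity (IG) sample by its ADA assay result and the PDR001 concentration at the same time. An assay-negative sample is ADA-inconclusive if "PDR001 PK concentration at the time of IG sample collection is greater than or equal to the drug tolerance level or missing". A determinant sample is defined as "Sample that is neither ADA-inconclusive nor unevaluable". A positive sample carries no PK condition: it is simply a "Determinant sample where assay is ADA positive". The same section defines the drug tolerance level as the highest concentration that does not disturb ADA detection, so the purpose of the PK condition is clear.

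The note that follows has two parts. PK values flagged for exclusion are still used to classify samples, but "the PK concentrations that are out of long term stability will be excluded from any IG analyses".

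Two summaries depend on this classification. The incidence set (SAP 2.3.7) takes patients "with a determinant baseline IG sample and at least one determinant post-baseline IG sample", and Table 2-1 removes anyone with "No determinant IG sample at baseline or post- baseline or both". Prevalence is reported overall and by time point, baseline included; by time point, "the denominator is the number of subjects at that time point with a determinant sample".

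Protocol Tables 7-6 and 7-7 schedule one IG sample before treatment, at Cycle 1 Day 1 pre-dose. Emergence of anti-PDR001 antibodies is a secondary objective (Protocol Table 3-1, SAP Table 1-1).

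**The concern.** The PK condition makes sense only where drug might be present to mask antibodies. Before the first infusion none can be. The study is first-in-human (Protocol 2.1), so no patient has had PDR001 before, and exclusion criterion 14 (Protocol 5.3) rules out other PD-1/PD-L1 agents. A missing PK value at that visit therefore casts no doubt on a negative ADA result. The SAP rule nevertheless applies to every sample without distinction.

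Two things follow. A patient with a valid negative baseline but no usable PK value has no determinant baseline and leaves the incidence set, whatever the later samples show. With only one scheduled pre-treatment IG sample, that baseline cannot be replaced. Also, at baseline, negatives leave the prevalence denominator while positives stay in numerator and denominator.

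**Working it through.** The documents give no ADA rate, no drug tolerance level and no rate of missing PK, so there is no planned figure to reproduce. The check has two parts.

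**1. The rule, case by case (SAP 3.8.1.1)**

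| ADA assay | PK below tolerance | PK at or above tolerance | PK missing |
|---|---|---|---|
| Positive | determinant | determinant | determinant |
| Negative | determinant | inconclusive | **inconclusive** |
| Not available | unevaluable | unevaluable | unevaluable |

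Among samples with an assay result, missing PK removes negatives only. Before the first dose the true concentration is zero, so every assay-negative sample belongs in the first column. The bold cell is the misclassification.

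**2. Possible size**

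Inputs:
- N = 319 treated patients (Protocol, Amendment 08 study status). All are taken to have a baseline ADA result.
- p = true baseline ADA prevalence: assumed 5%, with 2% and 10% as a range.
- m = share of pre-dose PK values missing or excluded, unrelated to ADA status: assumed 2%, 5% or 10%.

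Formulas:
- Patients losing a determinant baseline = N(1 − p)m
- Reported baseline prevalence = p / [p + (1 − p)(1 − m)]

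At p = 5%, N(1 − p) = 319 × 0.95 = 303.05.

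| m | Baselines lost (p = 5%) | Reported prevalence (p = 5%) | Baselines lost (p = 2% to 10%) |
|---|---|---|---|
| 2% | 303.05 × 0.02 = 6.1 | 0.05 / (0.05 + 0.931) = 5.1% | 6.3 to 5.7 |
| 5% | 303.05 × 0.05 = 15.2 | 0.05 / (0.05 + 0.9025) = 5.25% | 15.6 to 14.4 |
| 10% | 303.05 × 0.10 = 30.3 | 0.05 / (0.05 + 0.855) = 5.5% | 31.3 to 28.7 |

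The counts are upper limits for each m, because a patient must also have a determinant post-baseline sample to have been in the incidence set at all.

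**Effect on incidence.** Assume 5% of baseline-negative patients become treatment-induced positive and no baseline-positive patient is boosted.
- The treatment-induced rate has baseline-negative patients as its denominator. Numerator and denominator both shrink by (1 − m), so it stays at 5%.
- Overall ADA incidence with every baseline kept is 0.05 × 303.05 / 319 = 4.75%.
- At m = 5% it is 0.05 × 287.9 / (287.9 + 15.95) = 4.74%. At m = 10% it is 0.05 × 272.7 / (272.7 + 15.95) = 4.72%.
- The standard error of the treatment-induced rate grows by 1/√(1 − m): factors of 1.01, 1.03 and 1.05 at m = 2%, 5% and 10%.

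**The case against.** The best case against is that the affected group is probably small:
- Where both are measured, PK and IG come from a single blood sample (Protocol 7.2.3.2), so an ADA result without any PK draw should be uncommon.
- Values below the limit of quantification are set to zero (SAP 3.6), so an ordinary drug-free pre-dose result counts as zero and is not missing.
- PK values flagged for exclusion still serve to classify ADA samples (SAP 3.8.1.1, note).

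All of this stands. It leaves two routes: a failed PK measurement, or a PK result out of long-term stability. Both are possible, because the sample is split into aliquots and the two analytes are run on different assays (Protocol 7.2.3.1 and 7.2.3.2). That a value excluded for stability then counts as missing is a reasonable inference, but the SAP does not say so.

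A reader might also infer more than the documents support:
- *That prevalence at later time points is biased upward too.* After dosing, a negative result without a PK value may be masked by drug, and calling it inconclusive is defensible. Using all samples with an ADA result as the denominator would count possibly masked samples as negative and could bias prevalence downward.
- *That incidence is biased because true treatment-induced cases are lost.* Such cases are lost, but so are patients who stay negative, in the same proportion if missingness is unrelated to outcome.
- *That a large part of the study is affected.* At 20% missing the formula gives 0.20 × 303.05 = 60.6, about 61 of 319. Nothing in the documents supports a rate that high, and the figure would still be an upper limit.

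**Conclusion.** The point holds as a narrow gap in a definition. As written, SAP 3.8.1.1 misclassifies a pre-first-dose negative sample that has no PK value, and nothing else in the Protocol or SAP corrects it. The consequences are avoidable loss of patients from the incidence set and a slight overstatement of baseline ADA prevalence.

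The frequency is unknown and may be very low. Under the assumed 2% to 10% of missing pre-dose PK values and 5% prevalence, the loss is at most about 6 to 30 of 319 baselines, and the prevalence overstatement is about 0.1 to 0.5 percentage points. Incidence estimates lose some precision and are not clearly biased; that rests on missingness being unrelated to ADA outcome. These are descriptive summaries with no decision rule attached, so this is a minor correction, worth making because it is nearly free and cannot let a masked sample through.

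**What to change.** Add to SAP 3.8.1.1, after the definition of an ADA-inconclusive sample:

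*For samples taken before the first dose of PDR001, the PDR001 concentration is taken as zero when the PK value is missing or excluded; an ADA-negative result is then determinant and ADA-negative.*

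Naming excluded values as well as missing ones also settles how PK results out of long-term stability are treated at baseline. Leave the post-baseline rule and all denominators unchanged.

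The cost is one sentence, one line in the derivation, and the amendment or addendum that SAP section 1 requires for any change to the planned analysis. No new samples or assays are needed. Under the new rule no patient loses a determinant baseline solely because a PK value is missing.

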3.8.1.2 Subject ADA status

Any IG sample collected after 150 days of the last dose of PDR001 will not be used for summaries or derivations and will only be included in the listing.

Subject ADA status is defined as follows:

[figure not shown]
- *Treatment-induced ADA-positive subject*: subject with ADA-negative sample at baseline and at least one treatment-induced ADA-positive sample.
- *Treatment-boosted ADA-positive subject*: subject with ADA-positive sample at baseline and at least one treatment-boosted ADA-positive sample.

- *Treatment-unaffected ADA-positive subject*: subject with ADA-positive sample at baseline, no treatment-boosted ADA-positive samples, and at least one treatment-unaffected ADA-positive sample.
- *Treatment-reduced ADA-positive subject*: subject with ADA-positive sample at baseline and at least one post baseline determinant sample, all of which are ADA-negative samples.
- *ADA-negative subject*: subject with ADA-negative sample at baseline and at least one post baseline determinant sample, all of which are ADA-negative samples.
- *Inconclusive subject*: subject who does not qualify as treatment-induced ADA-positive, treatment-boosted ADA-positive, treatment-unaffected ADA-positive, treatment-reduced ADA-positive, or ADA-negative.

The following summaries of ADA subject status (n and %) will be provided using *Immunogenicity incidence set*:

- Treatment-boosted ADA-positive subjects; denominator is the number of subjects with ADA-positive sample at baseline.
- Treatment-induced ADA-positive subjects; denominator is the number of subjects with ADA-negative sample at baseline.
- ADA-negative subjects: denominator is the number of subjects in *Immunogenicity* incidence set.
- ADA-positive subjects (i.e. ADA incidence): calculated as the number of treatment-boosted ADA-positive and treatment-induced ADA-positive subjects; denominator is the number of subjects in *Immunogenicity incidence set*.

Listings will be provided of subject ADA status.

4 Appendix

4.1 Imputation rules

4.1.1 AE, ConMeds and safety assessment date imputation

Table 4-1 Imputation of start dates (AE, CM) and assessments (LB, EG, VS)

Missing Element	Rule
day, month, and year	No imputation will be done for completely missing dates
day, month	 If available year = year of study treatment start date then If stop date contains a full date and stop date is earlier than study treatment start date then set start date = 01JanYYYY Else set start date = study treatment start date. If available year > year of study treatment start date then 01JanYYYY If available year < year of study treatment start date then 01JulYYYY
day	 If available month and year = month and year of study treatment start date then If stop date contains a full date and stop date is earlier than study treatment start date then set start date= 01MONYYYY. Else set start date = study treatment start date. If available month and year > month and year of study treatment start date then 01MONYYYY If available month and year < month year of study treatment start date then 15MONYYYY

Any AEs and CMs with partial/missing dates will be displayed as such in the data listings. Any AEs and CMs which are continuing as per data cut-off will be shown as 'ongoing' rather than the end date provided. No imputation will be performed for AEs and CMs end dates.

4.1.2 Other imputations

Incomplete date of initial diagnosis of cancer and date of most recent recurrence

Missing day is defaulted to the 15th of the month and missing month and day is defaulted to 01-Jan.

Incomplete assessment dates for tumor assessment

All investigation dates (e.g. MRI scan, CT scan) must be completed with day, month and year. If one or more assessment dates are incomplete but other investigation dates are available, and if the overall response at that assessment is CR/PR/SD/UNK, this/these incomplete date(s) are

not considered for calculation of the assessment date and assessment date is calculated as the latest of all investigation dates (e.g. MRI scan, CT scan). Otherwise – if overall response is progression – the assessment date is calculated as the earliest date of all investigation dates at that evaluation number. If all measurement dates have no day recorded, the 1st of the month is used. If the month is not completed, for any of the investigations, the respective assessment will be considered to be at the date which is exactly between previous and following assessment. If previous and following assessment are not available, this assessment will not be used for any calculation.

Applying the cut-off to tumor assessment

For tumor related assessments, if an evaluation has some assessments done prior to cut-off date and others after the cut-off date, then the evaluation is considered post-cut-off date and will be excluded from analysis.

Prior anti-neoplastic therapy

Start date:

The same rule which is applied to the imputation of AE/concomitant medication start date will be used except it is set to be study treatment start date -1 if available year = year of study treatment start date and stop date is not a full date or not earlier than study treatment start date or if available month and year = month and year of study treatment start date and stop date is not a full date or not earlier than study treatment start date.

End date:

Imputed date = min (start date of study treatment, last day of the month), if day is missing;

Imputed date = min (start date of study treatment, 31DEC), if month and day are missing.

If the end date is not missing and the imputed start date is after the end date, use the end date as the imputed start date.

If both the start date and the end date are imputed and if the imputed start date is after the imputed end date, use the imputed end date as the imputation for the start date.

Missing death date

For cases when either day is missing or both month and day are missing for the date of death, the following imputation rules will be implemented:

- If only day is missing, then impute max [(1 mmm-yyyy), min (last contact date + 1, cutoff date)].
- If both day and month are missing, then impute max [(1 Jan-yyyy, min (last contact date + 1, cut-off date)].

4.2 Definition and derivation rules for irRC

4.2.1 Total measurable disease burden

In irRC target and new measurable lesions are used to evaluate total measurable tumor burden (TMTB). TMTB is the sum of diameters (SOD) of all target and new measurable lesions. Similar to RECIST v1.1 where SOD of the target lesions is used for determination of target lesion response, for irRC TMTB is used for determination of target and new measurable lesion response.

4.2.1.1 Best percentage change from baseline in TMTB

Best percentage change from baseline in TMTB is defined as the percentage change from baseline to the smallest measured post-baseline TMTB occurring at or before the time of confirmed irPD.

4.2.2 Assessment of disease progression

To facilitate analysis, each assessment of progression is categorized as one of three types: pseudo progression, confirmed progression and unconfirmed progression.

4.2.2.1 Pseudo-progression

Subjects with a single irPD, followed by an assessment of irSD or better will be considered to have a pseudo-progression (pPD). For the purposes of analysis, pseudo-progressions are not treated as progression events.

